Based on an exploratory analysis of response for subjects in the 8-mg daily regimen in Study BLC2001, when a higher phosphate level of 7 mg/dL was used as the new threshold, a larger separation of clinical response was observed between subjects with serum phosphate \geq 7 mg/dL and <7 mg/dL (45.5 vs. 31.6% for ORR; 90.9% vs. 75% for DCR).

Hence, the clinical goal is to maximize the number of subjects reaching the new target phosphate level of 7 mg/dL in order to attain maximum and sustained target inhibition.

Clinical Safety

The 8-mg daily regimen from the ongoing Study BLC2001 was well tolerated and without significant treatment interruptions (approximately 10% to 15% anticipated early interruptions). Up-titration from the 8-mg daily regimen to the 9-mg daily regimen on Cycle 1 Day 14 in subjects with both serum phosphate level below 5.5 mg/dL (ie, suboptimal PD effect) and without significant drug-related toxicity (ie, Grade ≥ 2 toxicity or Grade ≥ 1 central serous retinopathy or retinal pigment epithelial detachments) is likely to have a good overall tolerability profile and increases the likelihood of improved efficacy.

Moreover, the observed safety of the 9-mg daily regimen in the completed Phase 1 Study EDI1001 did not raise concerns about prolonged hyperphosphatemia, and no soft-tissue calcification or electrolyte disturbance or endocrine abnormalities were reported. Similarly, in the ongoing Phase 2 study, no such abnormalities were observed. Therefore, a more aggressive approach to up-titration may be adopted, allowing up-titration in subjects whose Day 14 phosphate is below 7 mg/dL (instead of below 5.5 mg/dL) without concurrent temporary use of phosphate binder treatment, or

whose serum phosphate is between 7 and 9 mg/dL with concurrent temporary use of phosphate binder treatment (see Section 6.1).

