Among adolescents aged ≥ 15 to <18 years of age following the adult regimen, at week 6, which corresponds to the median time to response and time of peak serum phosphate level, the percentage of subjects within the target phosphate range was predicted to be 30.2%, compared to 21.6% in adults. The percentage of subjects ≥ 15 to <18 years of age above the safety threshold was predicted to be 11.7% compared to 6.9% in adults, and 20.4% of subjects were predicted to have their dose interrupted within the first 6 weeks compared to 13% in adults. These predictions suggest that among this older group of adolescents, following the same dosing regimen as adults is likely to be acceptable from both safety and efficacy perspectives.

Among adolescents aged ≥ 12 to <15 years of age, the adult regimen leads, on average, to 20.4% subjects above the target phosphate range, which is more than the 13.8% pre-specified 2-fold increase compared with the adult reference and was not deemed acceptable. A lower starting dose of 5 mg with up-titration to 6 mg and a starting dose of 6 mg with up-titration to 8 mg led to an acceptable proportion of subjects with phosphate levels above 9 mg/dL, while retaining a good proportion of subjects within the target phosphate range. The dosing algorithm was further refined to allow for 2 possible up-titrations. This would allow younger adolescents to potentially benefit from a wider spread of doses, between 5 and 8 mg. Up-titrations at Day 7 and 14 and up-titrations at Day 14 and 28 were tested. The proportion of adolescents within and above the target phosphate

range after refinement led to 39.5% of subjects within the target range, while maintaining the proportion below 13.8% for the 2-week up-titration (14.8% for the 1-week up-titration and 12.0% for the 2-week up-titration). The proportion of subjects whose dose was interrupted was predicted 27.8% and 24.7% for the 1- and 2-week scenario, respectively. As the 2-week interval allows PK and PD to reach steady-state and leads to satisfactory efficacy and safety proportions, a 5-6-8 mg dose regimen with up-titrations at Day 14 and Day 28 was selected as the recommended dose for adolescents \geq 12 to <15 years old. Note that the predicted proportion of up-titrated subjects is around 96% at Day 14 and 85% at Day 28 for the selected scenario with starting dose of 5 mg and 2-week up-titration to 6 and 8 mg.

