Instructions for up-titration of erdafitinib, in the absence of erdafitinib related toxicity, based on the serum phosphate level at Cycle 1 Day 14 are provided below and in Figure 5. For children aged ≥ 6 to <12 years and adolescents aged ≥ 12 to <15 years, an additional blood sample will be drawn at Cycle 2 Day 7 for determination of the serum phosphate level and the need for dose modification.

Subjects with a serum phosphate level higher than 9.00 mg/dL (>2.91 mmol/L) will withhold erdafitinib treatment, with at least weekly assessment of serum phosphate until it returns to less than 7.00 mg/dL (<2.25 mmol/L) while initiating treatment with a phosphate binder such as sevelamer (see Table 8 for detailed guidelines regarding further treatment).

[figure not shown]

Figure 5: Instructions for up-titration of erdafitinib based on serum phosphate levels

Note: in presence of erdafitinib-related toxicities, the investigator may choose to maintain the same dose of erdafitinib without up-titration.

Adult subjects and adolescent subjects aged ≥ 15 to <18 years

- Adult subjects and adolescent subjects aged ≥15 to <18 years with a serum phosphate level between 7.00 to 8.99 mg/dL (2.25 mmol/L to 2.90 mmol/L) on Cycle 1 Day 14 will increase the erdafitinib dose from 8 mg once daily to 9 mg once daily, while concurrently initiating treatment with a phosphate binder such as sevelamer (see Table 8 for details).
- Adult subjects and adolescent subjects aged ≥15 to <18 years with a serum phosphate level less than 7.00 mg/dL (<2.25 mmol/L) will increase the erdafitinib dose to 9 mg once daily. No concomitant treatment is required for these subjects.

Adolescent subjects aged ≥ 12 to <15 years

- Adolescent subjects aged ≥12 to <15 years with a serum phosphate level between 7.00 to 8.99 mg/dL (2.25 mmol/L to 2.90 mmol/L) will increase the erdafitinib dose from 5 mg once daily to 6 mg once daily on Cycle 1 Day 14 or Cycle 2 Day 7, and further from 6 mg once daily to 8 mg once daily on Cycle 2 Day 7 (for those already up-titrated to 6 mg on Cycle 1 Day 14), while concurrently initiating treatment with a phosphate binder such as sevelamer (see Table 8 for details). This 2-step up-titration is step-wise, ie, no subjects will be allowed to directly up-titrate from 5 mg to 8 mg.

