8.2.2. Continuation of Treatment After Disease Progression

If the site study team makes an initial assessment of disease progression, and if the subject is clinically stable, treatment with erdafitinib may be continued. In the case of imaging-based progression (RECIST, Version 1.1 or RANO-defined disease progression) subjects may continue to receive erdafitinib treatment if the investigator and sponsor's clinical team agree and if the subject is clinically stable as defined by the following criteria: absence of signs and symptoms indicating overt disease progression, stable ECOG Performance Status grade (a comparison chart of ECOG, Karnofsky, and Lansky performance scores is provided in Section 10.6), absence of progressive tumor at critical anatomical sites (eg, spinal cord compression, new brain metastases) requiring urgent alternative medical intervention. Repeat tumor imaging at least 4 weeks but no later than 6 weeks after the first tumor imaging indicating progressive disease.

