2.3. Definition of Subgroups

Subgroup analysis will be performed for Broad Panel Cohort and Cholangiocarcinoma Expansion Cohort for the selected variables to assess the internal consistency of efficacy and/or safety. The subgroup variables and the cutoff values listed in [Table 2](#) are subject to change if warranted to better represent the data.

Subgroup analysis for countries/regions (e.g. China, East Asia) may also be performed.

Table 2: Subgroup Definition

Subgroup	Definition of Subgroup
Age	≥ 6 to < 12 years (applicable to the Pediatric Cohort only), ≥ 12 to < 18 years, ≥ 18 to < 65 years, ≥ 65 years
Sex	Male, Female
ECOG	0, 1
Geography	North America, Europe, Rest of the World
Number of Lines of Prior Therapy	1, 2, ≥ 3
FGFR alteration type	Mutation, fusion
FGFR gene	FGFR1-4
Up-titration status	Yes, No
Maximum serum phosphate within first 3 months	< 7 mg/dL, ≥ 7 mg/dL

In addition, tumor histologies (with the pre-defined list in Table 3 or all observed tumor histologies), may also be used to define subgroups for efficacy and/or safety.

Table 3: List of Tumor Histologies for Futility and Cap

Number	Tumor Histologies
1	Cholangiocarcinoma (CCA)
2	High-grade glioma (HGG)
3	Squamous NSCLC (sqNSCLC)
4	Squamous cell head and neck cancers (HNSCC)
5	Gastric Cancer (GSTRC)
6	Breast Cancer (BRST)
7	Endometrial Cancer (EDMTL)
8	Low-grade glioma (LGG)

9	Ovarian Cancer (OVAR)
10	Non-squamous NSCLC (nonsqNSCLC)
11	Colorectal Cancer (CRC)
12	Pancreatic Cancer (PANCR)
13	Cervical Cancer (CRVX)
14	Esophageal (ESOPH)
15	Other

Note: The group Other will enroll on all other tumor histologies not listed. The group “Other” shares the same cap of approximately 30 and will be included in the BHM evaluation for information borrowing only but will not be deemed futile early in the interim analyses and will continue enrollment until cap is reached.

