5.2. Primary Efficacy Endpoint(s)

5.2.1. ORR assessed by IRC Definition

A subject's best objective response (BOR) is defined as the best objective response a subject achieved during the study in the order of Complete Response (CR), Partial Response (PR), Stable Disease (SD), Progressive Disease (PD), where CR and PR are confirmed as per RECIST v1.1 or RANO. Responders are subjects with BOR of CR or PR. Subjects without measurable disease at baseline or without post-baseline tumor assessment are considered as non-responders.

ORR assessed by IRC is defined as the proportion of responders in an analysis population as assessed by IRC.

For the interim analysis (Interim I, II and III), a subject's BOR may also consider the unconfirmed Complete Response(uCR) and unconfirmed Partial Response(uPR). A subject's response will be classified as unconfirmed CR or PR if only one CR or PR has been observed and a subsequent valid disease evaluation has not been performed yet at the time of the interim analysis. However, a subject will be assigned SD/NE if the subject has only one CR or PR and has no subsequent

disease evaluation and is off study or started subsequent anti-cancer therapy. Two sets of analysis based on different definition of responder will be provided for DRC review for decision making:

- 1) Subjects with unconfirmed response (uCR or uPR) will be considered responders. However, subjects who have initially demonstrated a uCR or uPR but on subsequent evaluation have shown PD will not be considered responders.
- 2) Subjects with unconfirmed response (uCR or uPR) will not be considered as responders.

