5.2.3.4. Subgroup Analysis

Subgroup analyses for the ORR by IRC will be conducted for each subgroup (Section 2.3) within the Treated Population, respectively.

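### The ORR subgroup split on 3-month maximum phosphate has no landmark, so time on drug alone can favour the ≥7 mg/dL group

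*SAP*

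**What the plan says.** SAP 2.3 (Table 2) lists "Maximum serum phosphate within first 3 months" as a subgroup variable, cut at 7 mg/dL. It sets no landmark date, on-treatment condition or minimum number of readings. SAP 5.2.3.4 states that "Subgroup analyses for the ORR by IRC will be conducted for each subgroup" in the Treated Population. Under SAP 5.2.1, subjects "without post-baseline tumor assessment are considered as non-responders", and CR and PR must be confirmed. SAP 5.1.2 imputes no missing values unless otherwise specified.

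Protocol 4.3 describes results "at week 6, which corresponds to the median time to response and time of peak serum phosphate level", and states the clinical goal as to "maximize the number of subjects reaching the new target phosphate level of 7 mg/dL". SAP 2.3 presents the subgroups as a check of internal consistency and allows the variables and cut-offs to change.

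**The concern.** The grouping variable is a maximum taken after treatment starts, and the number of readings behind it depends on how long the subject stays on drug. Time on drug also goes with the outcome. A confirmed responder will usually remain under treatment and assessment past the first scan, while a subject who leaves at or before that scan is likely a non-responder. Early leavers therefore have fewer chances to reach 7 mg/dL, and they lower the ORR of the <7 mg/dL group. This is immortal-time bias.

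The cut is the same 7 mg/dL that the protocol names as its phosphate target. A gap in favour of ≥7 mg/dL would easily be read as support for that target when part of it may reflect follow-up alone.

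**Working it through.** The plan gives no figure for this contrast, so there is none to reproduce. The check has three parts.

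**1. Readings available.** Phosphate is in the chemistry panel (Protocol 10.2). Adult chemistry falls on Days 1 and 14 of Cycles 1–3, then on Day 1 of each cycle (Protocol 1.3). On-treatment readings within 3 months are on Days 14, 22, 35, 43, 56, 64 and 85, so 7 in all. A subject stopping at the week-6 scan has at most 4. The End-of-Treatment sample, 30 (+7) days after the last dose, adds one at about Day 73–80 for a Day-43 stopper. An earlier stopper may have no on-drug reading at the week-6 peak.

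**2. Simulated gap with no true association.**

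Inputs from Protocol 4.3:
- At week 6, 21.6% of adults are predicted in the 7–9 mg/dL range and 6.9% above 9 mg/dL ("above the safety threshold was predicted to be 11.7% compared to 6.9% in adults"), so 21.6 + 6.9 = 28.5% are at or above 7.
- A normal distribution through those two points has SD = 2/(z(0.931) − z(0.715)) = 2.19 and mean = 7 − 0.568 × 2.19 = 5.76 mg/dL.
- Baseline is 3.3 mg/dL.

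ORR is set at 15–35%, from the null rate to the target rate (SAP 1.3).

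Assumptions not in the documents:
- 33% of non-responders leave, around the first scan (Days 36–50) or, for an early share, on Days 1–35.
- Within-subject correlation is 0.3–0.7.
- 75/87/97/100% of the phosphate rise is reached by Days 14/22/35/43, then a fall to 90% or 75% of it by Day 85.
- Response and leaving are both unrelated to phosphate.

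The End-of-Treatment sample is left out of this base model. ORR gap favouring ≥7 mg/dL, in points, over ORR 15–35%:

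| Early leavers (before Day 36) | None continue past progression | 30% continue |
|---|---|---|
| None | 1.5–6.6 | 1.3–5.0 |
| A quarter | 2.8–9.3 | 2.4–8.5 |
| Half | 3.8–12.2 | 3.5–11.7 |

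The right-hand column reflects Protocol 8.2.2, under which, after imaging-based progression, "subjects may continue to receive erdafitinib treatment if the investigator" and the sponsor's clinical team agree and the subject is clinically stable.

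Central case (ORR 25%, correlation 0.5, slow fall, no early leavers): 26.8% vs 22.7%, a gap of 4.0 points before rounding. Variations on it:
- 30% continuing past progression: 2.8 points.
- A quarter leaving early: 5.9 points.
- End-of-Treatment sample added at 25–75% of the on-drug rise (assumed): about 3.0–3.6 points. If phosphate has mostly returned to baseline by then, the gap stays near 4.0.
- 10–30% of subjects exceeding 9 mg/dL by Day 43 made non-responders, to mimic stopping for toxicity (assumed): 3.1 down to 1.8 points.

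At ORR 25%, losses of 20% and 40% instead of 33% give 1.1–4.9 and 2.1–9.1 points.

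A second simulation used lognormal phosphate fitted to the same two percentages, correlation 0.6–0.9, and 5–15% of treated subjects stopping before week 6, with further non-responders stopping from the week-6 scan on. It gave 1.7–8.7 points at ORR 35% and 1.3–6.3 at ORR 25%. A harsher version, with exponential dropout from Day 1, gave 3–19.

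**3. Day-43 landmark and sampling error.** Landmark groups differed by less than 0.5 points in every setting of the first model. With 240 subjects split 108/132 (assumed) at ORR 25%, the 95% half-width of the difference is 1.96 × √(0.25 × 0.75 × (1/108 + 1/132)) = 0.110, or 11 points.

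**The case against.** The strongest counter-case concerns size and consequence, and much of it stands.

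- **The size is assumed.** Loss rate, timing, correlation and time course have no source in the documents. The normal fit also puts about 13% of subjects below the 3.3 mg/dL baseline at the peak. With SD 1.0 or 1.4 instead, the gap is 1.5–9.6 points at 33% loss, none or a quarter early and none continuing. The range is therefore not a product of that fit, but it remains illustrative.
- **The direction is not certain.** Drug is withheld above 9 mg/dL and stopped permanently for some persistent elevations and toxicities (Protocol 6.1, 6.6). Non-responders created in that way fall in the ≥7 mg/dL group and pull against the bias.
- **The near-zero landmark gap is built in.** It follows from making response and leaving independent of phosphate. It shows that the landmark removes the follow-up artefact, not that no other link exists.
- **A landmark changes the population.** It drops mostly non-responders, so both groups' ORRs rise above the Treated Population figure. Day 43 is also the nominal scan visit, so inclusion can turn on a day's difference in the recorded date. In the simulation, first-scan leavers were spread over Days 36–50 and the gap did not return.
- **The consequence is small.** The row carries no alpha, and exposure-response work is a separate exploratory objective.

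A reader might go further and infer that the primary result is biased, that any observed gap would be wholly spurious, or that the dose target is undermined. The documents support none of these. The primary test pools histologies without reference to phosphate. A real association may exist alongside the artefact. The dose rationale in Protocol 4.3 rests on earlier studies and modelling, and no passage makes this row a basis for dosing.

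**Conclusion.** The point holds as a minor one. As written, the rule gives subjects unequal opportunity to enter the ≥7 mg/dL group and keeps the shortest-followed subjects in the denominator, mostly as non-responders. With no true association, that tends to favour ≥7 mg/dL.

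The illustrative size is roughly 1–9 points. Values of 12 or more need heavy early dropout, for which the documents give no support. The End-of-Treatment sample and toxicity-driven stopping reduce the gap. The expected bias is smaller than the row's own sampling error of about 11 points, but it is systematic and simple to remove.

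The structural part rests on the documents alone. The size rests on assumed loss rates, phosphate correlation and time course, and on leavers being non-responders.

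**What to change.** In SAP Table 2, define the row as maximum serum phosphate through Cycle 3 Day 1 (Day 43), <7 or ≥7 mg/dL, in subjects not permanently discontinued from study drug by Day 43. Count subjects whose drug is temporarily interrupted or withheld on that day as on treatment. The protocol says "Subjects with a serum phosphate level higher than 9.00 mg/dL (>2.91 mmol/L) will withhold erdafitinib treatment", and 6.9/28.5 = 24% of the week-6 ≥7 mg/dL group are predicted above 9 mg/dL, so excluding them would strip that group.

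Also:
- Label the row post-baseline and exploratory.
- Tabulate subjects discontinued by Day 43, with their responses, separately.
- Keep the 3-month row beside it, if wanted, under the same label.
- Give the up-titration status row the post-baseline label too, since it is also set after treatment starts.
- Footnote that the two landmark groups are to be compared with each other and not with the overall ORR.

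The cost is a SAP table edit on data already scheduled, which SAP 2.3 already permits. The downside is that about 9–16% of subjects leave the row (ORR 25%, 33% loss assumed). If all are non-responders, the landmark ORR becomes 25/0.91 = 27.5% to 25/0.84 = 29.8%, about 2.5–5 points above the Treated Population ORR.

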2.4. Study Day and Relative Day

A treated cycle for a specific drug is defined as a cycle in which the subject received any amount of the specific drug. The cycle number will be named according to the sequence of every 21-day cycle for study agent administration.

Assessments will be presented chronologically by study day or cycle day as described below:

Reference date (Day 1) = first dose date of study medication.

Study Day = assessment date – reference date + 1 for assessment performed on or after the reference date; or assessment date – reference date for assessment performed before the reference date.

Cycle Day = assessment date - date of the first dose for the cycle + 1.

There is no “Day 0”.

2.5. Baseline and Endpoint

Baseline is defined as the last non-missing observation prior to the start of the first dose of study drug.

Endpoint is defined as the last available postbaseline result within the analysis period. Unscheduled visit results are included in this definition and will be considered as the endpoint value if the unscheduled visit result is the last postbaseline result available within the analysis period.

2.6. Imputation Rules for Missing and Partial Dates

In general, imputation of missing dates will be made for AE onset date, AE resolution date, date of death, start and end dates of concomitant and subsequent therapies, and date of initial diagnosis according to the following rules. Start date will be imputed before end date.

- If date is completely missing, no imputation will be made.
- If year is missing, no imputation will be made.
- If only year is present but month and day are missing, then June 30th will be used.
- If only day is missing but year and month are available, then the 15th of the month will be used.

However, the above imputations will be modified by the following rules:

- If such imputed date for initial diagnosis is on or after the first dose date, then the first dose date - 1 will be used.
- The imputed start date for subsequent therapies will be adjusted sequentially using the following steps:
 - If the imputed start date is before the treatment discontinuation date (or last dose date if no treatment discontinuation date) but in the same year and month, then the treatment discontinuation date (or last dose date if no treatment discontinuation date) will be used.
 - If subsequent therapy end date is not missing and is before the imputed subsequent therapy start date, then the subsequent therapy end date will be used as the start date.
- If the imputed date is for a date of death and is before the last date that the subject is known to be alive, the latter date will be used.
- The imputed AE start date will be adjusted sequentially using the following steps:
 - If the imputed date is in the same year and month as but day before the first dose date, then the first dose date will be used, or if it is in the same year and month as but day after the last dose date + 30 days, then the last dose date + 30 days will be used.
 - If AE end date is not missing and the imputed AE start date is after the AE end date, then the AE end date will be used.
 - If the imputed AE start date and is after date of death, then date of death will be used
 - If the imputed AE start date is in the same month and year but after the 1st subsequent therapy start date, then 1st subsequent therapy start date will be used.
- If the imputed date is for an AE end date and is after the death date, then the death date will be used, or if the imputed AE end date is before the AE start date, then the AE start date will be used.
- The AE imputation rule will be used for concomitant medication.

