5.2.2. Estimand

The primary estimand, the main clinical quantity of interest to be estimated in this study, is defined by the following four components (ICH E9 (R1) Addendum, 2018):

- Population: subjects with advanced solid tumors and target FGFR Gene Alterations.
- Variable: subject responder status (responder – BOR of CR or PR; otherwise – non-responder).
- Intercurrent events: treatment discontinuation and subsequent anti-cancer therapy. The treatment policy strategy will be applied to account for the treatment discontinuation. That is, the value for the variable of interest is used regardless of whether the treatment discontinuation occurs. The while-on-treatment policy will be applied to account for subsequent anti-cancer therapy. That is, only the value for the variable of interest before the subsequent anti-cancer therapy will be used. For instance, if a subject discontinued study treatment but did not start subsequent anti-cancer therapy, the subject's responder status/tumor assessment will be used as if the subject is still on treatment regardless of the treatment discontinuation (i.e. the treatment policy). But if a subject started subsequent anti-cancer therapy, no matter whether the subject has discontinued treatment or not, the subject's responder status/tumor assessment after the subsequent anti-cancer therapy will not be used in the analysis (the while-on-treatment policy).
- Population-level summary: ORR assessed by IRC.

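### SAP 2.6 sets year-only dates to 30 June, and its same-month condition means AE onset and subsequent-therapy start are never moved up to a first dose or stop in July to December

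*SAP*

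**What the plan says.** SAP 2.6 (Imputation Rules for Missing and Partial Dates) covers AE onset, subsequent-therapy start and several other dates. When only the year is known: "If only year is present but month and day are missing, then June 30th will be used". When only the day is missing, the 15th of the month is used. Corrections follow.

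- **AE onset, lower bound.** "If the imputed date is in the same year and month as but day before the first dose date, then the first dose date" is substituted. A matching upper bound uses last dose + 30 days, again only within the same year and month. A later step against the first subsequent therapy has the same month condition.
- **Subsequent-therapy start.** The rule opens "If the imputed start date is before the treatment discontinuation date" and goes on "or last dose date if no treatment discontinuation date) but in the same year and month"; the discontinuation or last dose date then replaces the imputed one.
- **Concomitant medication** takes over the AE rule.
- **Initial diagnosis and death.** Their corrections carry no month condition.

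These dates are used downstream. SAP 6.1.2 decides treatment-emergent status from the imputed AE onset and ends the TEAE period the day before subsequent anticancer therapy, if that comes first. For the primary ORR estimand, SAP 5.2.2 states that "only the value for the variable of interest before the subsequent anti-cancer therapy will be used". SAP 5.3.2 and 5.3.5 censor DOR and PFS at the last assessment before subsequent therapy when progression or death follows that therapy.

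**The concern.** The month condition suits day-missing dates, where the imputed 15th may fall a few days before a first dose in the same month. It does not suit year-only dates, where the imputed month is always June whatever the subject's treatment dates. An AE that occurred on treatment can then be dated before treatment, and a therapy given after erdafitinib can be dated months before erdafitinib stopped.

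The resulting dates sit badly with the protocol. AEs are collected from the full-study consent (Protocol 8.4.1), normally within the 30-day screening period (Protocol 8.1.1.2). Concurrent antineoplastic agents are prohibited during treatment (Protocol 6.5.2). At stake are TEAE counts, responder status and two censoring rules, all in a rule fixed in advance that programmers are expected to follow literally.

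**Working it through.** The plan gives no figure on this point, so there is none to reproduce. The check applies the SAP 2.6 rules as written.

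1. **Can the lower-bound corrections act on a year-only date?** Both need the imputed date to share year and month with the reference date and to be earlier. The imputed date is 30 June, so the reference date would have to be in June and after the 30th. No such date exists. Running the rules for every calendar day as first dose, and then as discontinuation, gives 0 of 366 days (2020) and 0 of 365 days (2021) on which either correction is triggered.

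2. **On which days does this leave a misplaced date?** Reference dates from 1 July to 31 December: 31 + 31 + 30 + 31 + 30 + 31 = 184 days. 184/365 = 50.4% (2021); 184/366 = 50.3% (2020). This is a share of calendar days.

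3. **Examples.**
   - First dose 10 September 2020, AE recorded as 2020: onset becomes 30 June 2020, which is 31 + 31 + 10 = 72 days before first dose.
   - Discontinuation 15 October 2021, therapy recorded as 2021: start becomes 30 June 2021, which is 31 + 31 + 30 + 15 = 107 days before treatment ended.

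4. **Do later steps repair it?** The AE end-date step ("If AE end date is not missing and the imputed AE start date is after the AE end date") and the therapy end-date step ("If subsequent therapy end date is not missing and is before the imputed subsequent therapy start date") have no month condition but can only move a start earlier. The death-date and first-subsequent-therapy steps for AEs also only move it earlier.

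5. **Upper side.** If last dose + 30 days falls from 1 January to 31 May (151 days in 2021), a year-only AE of that year is dated after the window and is not pulled back. Last dose 10 February 2021 gives a window end of 12 March 2021; the AE becomes 30 June 2021. This correction does work when the window ends on 1 to 29 June.

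6. **When do results change?**
   - *TEAE status.* Drug-related AEs count whatever their date, and AEs that worsen in the TEAE period also count (SAP 6.1.2). What can drop out is an AE judged unrelated that does not meet the worsening criterion. A therapy start set too early also shortens the TEAE period, so correctly dated unrelated AEs can be lost too.
   - *ORR.* Response is the best confirmed response (SAP 5.2.1). A response confirmed before 30 June is kept; one first documented or confirmed between 30 June and the true therapy start is lost. With first dose in August 2021, stop in December 2021 and therapy recorded as 2021, every post-baseline scan falls after the imputed therapy start, so a true responder becomes a non-responder.
   - *DOR and PFS.* Censoring moves earlier only for subjects whose progression or death falls after the imputed start.

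**The case against.** The strongest reply is that such dates will be rare. AEs are reported prospectively from consent to 30 days after last dose (Protocol 8.4.1), with visits in every 21-day cycle. Subsequent therapy is asked about every 12 weeks (Protocol 8.1.4), and queries can be raised in the data-capture system (Protocol 10.3.9). A date known only to the year should be uncommon for events after enrolment. This stands, and it is why the point is minor.

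A second reply is that SAP 5.1.2 leaves other data handling rules to a separate specification, which is not available here. That document might add a safeguard, but it would be adding to an explicit rule that points the other way, so the SAP wording still needs correcting.

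A reader might also infer more than the documents support:

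- That every date correction in SAP 2.6 shares the flaw. It does not: the corrections for initial diagnosis, death, AE end and therapy end carry no month condition.
- That on-treatment AEs drop out generally. The drug-related and worsening criteria keep many of them as TEAEs, although their onset dates remain wrong.
- That half, or a quarter, of subjects or records are misdated. Among same-year year-only records alone, the share depends on the weighting. One record per subject with stop dates spread evenly over the year gives 184/365 = 50.4% and a mean gap of (1 + 184)/2 = 92.5 days. Weighting by time left in the year gives (184 × 185/2)/(365 × 366/2) = 17,020/66,795 = 25.5% and a mean gap of about 62 days. Neither is a share of the trial's patients.

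**Conclusion.** The rule is wrong as written. For year-only dates the two lower-bound corrections can never take effect. On 184 of 365 possible first-dose or stop dates, a year-only date from the same year is left before first dose or before treatment ended. This follows from the text alone, without any assumption about the data.

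The effect on results is conditional in each case and cannot be sized from the documents, because the number of year-only dates is not given and may be near zero. The documents do not support a claim that the ORR, DOR, PFS or TEAE results are materially biased. They do support the narrower statement that, for an affected subject, the rule can change responder status, TEAE status or a censoring date. Severity is low; the case for acting is that the correction is simple and can be specified in advance.

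**What to change.** In SAP 2.6, keep the present wording for day-missing dates. For dates with month and day missing, apply the corrections on year alone:

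1. If the imputed AE onset precedes first dose in the same year, use the first dose date.
2. If it is after last dose + 30 days in the same year, use last dose + 30 days.
3. Treat the AE step against the first subsequent therapy the same way. That step lands on the therapy start date, one day past the end of the TEAE period, so it tidies the onset date but does not itself change TEAE status.
4. If the imputed subsequent-therapy start precedes discontinuation (or last dose, if there is no discontinuation date) in the same year, use that date.
5. Keep the AE end-date, death-date and therapy end-date steps after these.
6. State whether the year-only first-dose adjustment applies to concomitant medication. If it is carried over unchanged, a medication truly begun before first dose would be moved to first dose.

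With items 1 and 4 in place, the calendar check falls from 184 of 365 misplaced dates to 0 for both AE onset and subsequent-therapy start. The cost is a few lines of SAP text and a small change to the date-imputation program.
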